5.2.3. Study Treatment

5.2.3.1. Treatment with RZL-012 Investigational Drug

RZL-012 or vehicle will be supplied as a single vial for a single treatment session per subject. Up to 48 injections will be dosed to 4-8 lipomas per each subject.

Overall dose, dosing regimen and injection technique is crucial for safety of study participants.

Syringes will be filled with the desired volume for injection of RZL-012 or vehicle. All injections will be administered at 90° to injected skin, using a 1 mL Luer-lock syringe and a 30 G x 1/2" needle.

The hole of the needle should be pointing into the fat layer. An attempt to pull the plunger should be made before injecting to ensure that no blood is coming out. If so, the plunger should be pushed down to inject the medicine. The formulation is viscous and therefore resistance is expected while injecting.

[figure not shown]
The injected volume will be calculated according to lipoma size (Table 3):

Table 3: Injected volume and dosages of RZL-012 / Placebo according to lipoma size

Number of Subjects – Active/Placebo	19/19				
Lipoma/Nodule size – diameter (cm)	1-1.9	2-3.9	4-5.9	6-7.9	8-10
Total Dose of RZL-012 in the RZL group (mg)	10	20	40	50	60
Number of Injections	2	4	8	10	12

Injections will be given perpendicular (90°) to injected skin surface towards the center of the nodule and the distance between injections in a nodule will be at least 1 cm (Figure 1). The dosing will be done in gradual injections of each 0.1mL into the tissue.

Figure 1: RZL-012/ Placebo Injection Sites in DD Subjects

Each RZL-012 kit contains 1 vial (250 mg/5 mL) enabling injection of the maximal dose per subject, 240mg. RZL-012 or vehicle will be injected on study Day 0 visit (baseline).

After completing injections of lipomas, an ice/cold pack will be applied onto the injection sites for immediate pain relief and will be held by the subject for at least 2 minutes. Following completion of injection procedures, subjects will remain in the clinic for an additional 2 hours ± 30 min for medical supervision and in order to follow adverse events after injection. During the stay in the clinic there are no restrictions in terms of activity or diet.

5.2.4. Treatment with Placebo

Nineteen (19) subjects randomly assigned to the study will be injected with placebo, which will be a vehicle control (tween-80, propylene glycol, benzyl alcohol and water) in the same manner as mentioned above (Section 5.2.3.1).

5.2.5. Baseline Visit

Baseline visit on day 0 will be performed to complete screening evaluation, and to review all procedures necessary to confirm subject eligibility prior to dosing. Subjects will stay under supervision in the study center for 2 hours \pm 30 minutes following drug injection.

Screening information may be considered for baseline data if acquired within the adequate timeframe as described in Table 4.

Information	Timeframe	Follow-up Timeframe
Informed Consent Form	Signed prior to any study dedicated procedure	
Medical History	At Screening Day visit	
RZL-012 dosing	At baseline (day 0)	
Concomitant Medications	At screening Day visit, Day 0, 1,7,28,56,84	
Physical examination	At Screening Day visit and at Days 28, 56	
Vital Signs	At Screening Day visit and at Days 0 (pre- and following injection), 1, 28, 56	
Pregnancy test (women only)	Will be performed at Baseline	
ECG	At screening, Day 1, 28	
Draize Score at the Injected Site	At Days 0 (pre- and following injection), 1, 28, 56	Day 84
Ultrasound for nodule size assessment	At Screening Day visit and at Days 0*, 28, 56	Day 84
Photography of the Injected Sites	At Screening Day visit and at Days 0*, 28, 56	Day 84
Pain assessment using Comparative Pain Scale	At Days 0, 28, 56	Day 84
QOL assessment	At day 0	Day 84
Serology assays (HbSAg, HCV and HIV)	At Screening Day visit	
Serum chemistry and Hematology	At Screening Day and at Days 1, 28	
Urinalysis	At Screening Day and at Days 1, 28	
Lipid Profile	At Screening Day and at Day 1	
AEs assessment	At Days 0, 1, 7, 28, 56	Day 84

Table 4: Subject Information and Timeframes for the Placebo controlled Phase of the Study:

* In case of screening visit that will be conducted only one day before Baseline, ultrasound at Baseline visit is optional. The ultrasound parameters and photography collected at screening will be used at Baseline visit.

Table 5: Subject Information and Timeframes for the Open Label Extension Phase:

Information	Timeframe	Follow-up Timeframe
RZL-012 dosing	At baseline (day 0)	
Concomitant Medications	At Day 0, 1,7,28,56,84	
Physical examination	At Day 0, 28, 56	

Information	Timeframe	Follow-up Timeframe
Vital Signs	At Days 0 (pre- and following injection), 1, 28, 56	
ECG	At Day 0, 1, 28	
Draize Score at the Injected Site	At Days 0 (pre- and following injection), 1, 28, 56	Day 84
Ultrasound for nodule size assessment	At Day 0 visit and at days 28, 56	Day 84
Photography of the Injected Sites	At Day 0 visit and at days 28, 56	Day 84
Pain assessment using Comparative Pain Scale	At Days 0, 28, 56	Day 84
QOL assessment	At day 0	Day 84
Serum chemistry and Hematology	At Day 0 and at Days 1, 28	
Urinalysis	At Day 0 and at Days 1, 28	
Lipid Profile	At Day 0 and at Day 1	
AEs assessment	At Days 0, 1, 7, 28, 56	Day 84

5.2.6. Subject Site Visits

Subject site visits will be performed ± 2 days from scheduled date (for study visit Days 28, 56 and 84). Day 7 phone call to the subject will be performed ± 1 day from scheduled day.

For site visits that result in study discontinuation, see termination visit in Section 5.2.7.

5.2.7. Termination Visit

Once study is discontinued, all reasonable measures should be taken to perform a termination visit. Termination visit should include all procedures necessary to complete subjects' records: AE reporting, evaluation of response and updating of subject contact information. An effort should be made to perform all activities conducted on visit Day 84 for subjects who participates in the double-blind randomized placebo controlled study.

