- Treatment - All injections will be administered 90° to the injected skin surface using a 1 mL Luer-lock syringe and a 30 G x 1/2" needle (the hole of the needle pointing into the fat
 layer). Post treatment: vital signs (2h ± 30 min post injection). evaluation of skin irritancy by Draize score (2h post injection ± 30 min), adverse events (AEs) will be recorded. *In case of screening visit that will be conducted only one day before Baseline, ultrasound and photographs at Baseline visit are optional. The ultrasound parameters collected at screening will be used at Baseline visit. Schedule visits (Day 1-56):
- Day 1 following treatment will include: ECG, vital signs including pulse rate, Draize score,
 Day 1 following treatment will include: ECC, vital signs including pulse rate, Draze score, clinical laboratory tests, urinalysis, lipid profile, AEs record. Subjects will start applying an anti-histamine gel. Day 7± 1d from treatment: Phone call for follow up. Day 28± 2d from treatment: ECG, physical exam, vital signs, clinical laboratory tests, urinalysis, Draize score, lipoma/nodule size assessment by ultrasound, clinical evaluation of local pain and tenderness to pressure, photographs, AEs record Day 56± 2d from treatment: physical examination, vital signs, Draize score, lipoma/nodule size assessment by ultrasound, clinical evaluation of local pain and tenderness to pressure, photographs, AEs record Day 84± 2d from treatment:
Draize score, photographs, assessment of lipomas/nodules size using US, clinical evaluation of local pain and tenderness to pressure, QOL questionnaire, AEs record.
In case a specific subject demonstrates elevated levels in one or more of the tested parameters, this subject will be followed up on day 56 to confirm return to normal levels.
Open Label Extension Phase: Following the opening of the randomization codes, placebo subjects will be offered the option of receiving treatment with RZL-012. Subjects who choose this will be followed up for an additional 84 days for efficacy and safety as described below:
The physician will set up a date for injection with RZL-012 within 30 days of codes opening. This will be the baseline visit, Day 0. The following procedures will take place on Day 0 visit:

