5.1.4. Physical Examination

The investigator (or medically qualified nominee) will conduct a complete physical examination, height and weight measurements at Screening Day (performed 14 through 1 day prior to baseline). Clinically significant abnormal findings except overweight and obesity should be discussed with the Sponsor.

Additional physical examination to assess subject's safety will be performed on study visit on Day 28 and 56 following treatment.

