5.1.7. Vital Signs Measurements

Subjects' vital signs will be measured at Screening Day (performed 14 through 1 day prior to baseline) in order to ensure compliance with study inclusion criteria.

Vital signs measurements will include systolic and diastolic sitting position blood pressure, pulse rate, respiratory rate, and body oral temperature.

Additional vital signs measurements to assess subject's safety will be performed on baseline visit (Day 0) prior to drug injection, $2h \pm 30$ min following drug injection, the following day (Day 1) after drug injection ($24h \pm 2h$) and on study visits Day 28 and Day 56 following injection.

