5.1.9.1. Hematology

Hematology tests will be conducted at Screening Day (performed 14 through 1 days prior to baseline) in order to ensure compliance with study inclusion criteria. Additional Hematology testing will be conducted to assess subject's safety on study visit Day 1 and Day 28 following injection.

Hematology tests will include Complete blood count (CBC) including White blood cell (WBC) differential values, D-dimer, Fibrinogen and coagulation (International normalized ratio (INR), Partial thromboplastin time (PTT) and Prothrombin time (PT)).

In case a specific subject demonstrates elevated blood levels in one or more of the tested parameters, this subject will be followed up on day 56 to confirm return to normal levels.

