5.1.15.2.2. Safety monitoring

Safety and tolerability will be assessed, according to definitions and guidelines, by the medical staff (e.g., PI, site coordinator, and study nurse) and the study subjects:

- 1. AEs and SAEs, including severity, relation to study treatment and classification by whether or not these events comprise intolerable side effects.
- 2. Physical exams, Draize score and vital signs measurements.
- 3. Urine testing.
- 4. Blood laboratory testing for changes in hematology and chemistry values.
- 5. Lipid profile.
- 6. ECG.

Subjects questioning - full medical history during screening, routine AE reporting and tolerability monitoring.

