6. DESCRIPTION OF THE OPEN LABEL EXTENSION PHASE OF THE STUDY

At study completion, the randomization codes will be opened. Nineteen (19) Subject who were injected with placebo will be offered to be treated with RZL-012.

At least 4 lipomas/nodules, preferably 6, and no more than 8, will be injected per subject. Dosing will be according to lipoma size, where the total injected dose will not exceed 240mg per patient (48 injections at 5mg/injection).

Dosing will be done according to lipoma size, as described in Table 6:

Table 6: Dosing of RZ-012 in the Open Label Extension Phase

Number of Subjects – Active/Placebo	19/19					
Lipoma/Nodule size – diameter (cm)	1-1.9	2-3.9	4-5.9	6-7.9	8-10	
Total Dose of RZL-012 in the RZL group (mg)	10	20	40	50	60	
Number of Injections	2	4	8	10	12	

The injection with RZL-012 will be done within 30 days of randomization codes opening.

The day that will be set up by the physician for RZL-012 injection will be the baseline visit, Day 0.

On this day, each subject will have the procedures, as described in Section 5.1:

Day 0- Physical exam, Clinical laboratory tests (hematology, chemistry) lipid profile and urinalysis, ECG, injection with RZL-012, concomitant medication, vital signs – before and after the injection, ultrasound measurement of the lipomas*, photography of the lipomas, QOL questionnaire, Draize score – before and after injection, pain score and AEs documentation.

Day 1 – ECG, vital signs, Draize score, clinical laboratory tests including urinalysis and lipid profile, AEs record.

Day 7 – Phone call visit. The study coordinator/nurse will call the subjects to ask about adverse events and general health.

Day $28\pm 2 - ECG$, physical exam, vital signs, clinical laboratory tests, urinalysis, Draize score, ultrasound measurement of the lipomas, photography of the lipomas, pain score and AEs documentation.

Day 56±2 - Physical exam, vital signs, ultrasound measurement of the lipomas, photography of the lipomas, Draize score, pain score and AEs documentation.

Day 84±2 - Ultrasound measurement of the lipomas, photography of the lipomas, QOL questionnaire, Draize score pain score, QOL questionnaire and AEs documentation.

Schedule of events of the open label extension part is presented in Appendix 2.

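### The termination visit in Section 5.2.7 is modelled on Day 84, so a subject leaving before Day 56 has no stated exit laboratory tests, urinalysis, ECG, vital signs or physical examination

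*Combined protocol and SAP*

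**What the plan says.** Section 5.2.7 describes the termination visit in two steps. The general content is: "Termination visit should include all procedures necessary to complete subjects' records: AE reporting, evaluation of response and updating of subject contact information". The template visit is then named: "An effort should be made to perform all activities conducted on visit Day 84 for subjects who participates in the double-blind" phase.

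The synopsis visit schedule gives Day 84 of the placebo-controlled phase as "Draize score, photographs, assessment of lipomas/nodules size using US, clinical evaluation of local pain and tenderness to pressure, QOL questionnaire, AEs record". Table 4 and Appendix I agree, and add concomitant medication. For the open label extension, Section 6 gives Day 84 as "Ultrasound measurement of the lipomas, photography of the lipomas, QOL questionnaire, Draize score pain score, QOL questionnaire and AEs documentation".

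Systemic safety tests are scheduled earlier. Section 5.1.4 says: "Additional physical examination to assess subject's safety will be performed on study visit on Day 28 and 56 following treatment". Under 5.1.7, post-dose vital signs are taken at 2 hours, on Day 1 "and on study visits Day 28 and Day 56 following injection". Hematology, chemistry, urinalysis and ECG fall on Days 1 and 28 after dosing (5.1.9.1 to 5.1.9.3, 5.1.10, Table 4). If a laboratory value is elevated, "this subject will be followed up on day 56 to confirm return to normal levels" (5.1.9.1). Day 7 is a telephone call.

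**The concern.** Day 84 is a sensible last visit for completers, because they already have their Day 28 and Day 56 safety data. It is a poor model for someone who leaves early, because it is the site visit from which these tests are absent. Read literally, 5.2.7 asks an early leaver for ultrasound, photographs and a quality-of-life form, but not for blood tests, an ECG, blood pressure or an examination.

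At stake are the safety monitoring of individual leavers and the completeness of the safety data. Section 5.1.14 makes physical examination, vital signs and blood tests part of the basis for identifying adverse events. Section 5.1.9 has laboratory changes from baseline, judged against normal ranges, documented as adverse events. A test that is not done cannot produce such an event, so adverse event ascertainment in leavers may be reduced as well as the laboratory, ECG and vital-sign summaries. The planned maximum dose is 240 mg, 33% above the highest dose given to humans (Section 2.4).

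**Working it through.** The plan gives no figure to reproduce. The check is a comparison of schedules and a count.

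**Inputs** (Table 4, Appendix I, Sections 5.1.4, 5.1.7, 5.1.9.1 to 5.1.9.3, 5.1.10). Scheduled post-dose times:

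- Laboratory tests (hematology, chemistry), urinalysis and ECG: Days 1 and 28, so 2.
- Vital signs: 2 hours and Days 1, 28 and 56, so 4.
- Physical examination: Days 28 and 56, so 2.
- On Day 84: none of these.

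**Count.** As written, the minimum is the number of scheduled times already passed at exit, plus 0 from the Day 84 template. With the fix, one set of the assessments not yet done is added, provided that the subject attends.

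| Exit | Assessment | Minimum as written | With the fix, if the visit is attended |
|---|---|---|---|
| Between Day 1 and Day 28 | Labs, urinalysis, ECG | 1 of 2 | 1 + 1 = 2 of 2 |
| | Vital signs | 2 of 4 | 2 + 1 = 3 of 4 |
| | Physical examination | 0 of 2 | 0 + 1 = 1 of 2 |
| Between Day 28 and Day 56 | Labs, urinalysis, ECG | 2 of 2 | 2 of 2, plus recheck of any elevated laboratory value |
| | Vital signs | 3 of 4 | 3 + 1 = 4 of 4 |
| | Physical examination | 1 of 2 | 1 + 1 = 2 of 2 |
| After Day 56 | All of these | complete | unchanged |

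The two windows last 28 − 1 = 27 days and 56 − 28 = 28 days, or 27/84 = 32% and 28/84 = 33% of follow-up. These are calendar fractions, not risks of leaving.

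**Does another rule supply the tests?**

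- Section 4.4: leavers are followed as far as possible, and those with serious side effects until the event resolves or is stable. No test is named.
- Section 9.4.1: serious or severe adverse drug reactions must be clinically evaluated, and adverse drug reactions are followed to resolution or for at most 6 months. Both start from an event already recognised.
- Section 5.2.8: unscheduled visits may repeat unusual results or complete missing ones. They depend on the investigator's judgement, a sponsor request or the subject's decision.
- Section 11.1: final evaluations are to be attempted at any withdrawal. The natural reading points back to the final visit, Day 84.

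None of these requires a named set of tests at exit.

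**Extension phase.** Table 5 and Appendix I place the same post-dose tests on the same days, so the gap recurs. The Day 84 sentence in 5.2.7 refers only to double-blind subjects, so extension leavers have no template visit at all.

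**The case against.** The strongest reply is that the protocol already has a working withdrawal framework, and much of this stands. Section 5.2.8 expressly provides for repeating unusual results and completing missing ones, so it would be wrong to infer that an elevated value in a leaver cannot be rechecked. Under 5.1.9 a physician assesses every out-of-range value, and a resulting adverse drug reaction is followed under 9.4.1. A subject who stops at a scheduled Day 28 or Day 56 visit would also be due that visit's own procedures. What remains is the new or silent abnormality in someone who leaves between visits.

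A reader might also infer that the exit visit has no safety content. It does: Section 5.1.15.2.2 counts "Physical exams, Draize score and vital signs measurements" among the safety assessments, and Day 84 retains the Draize score and adverse event recording.

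Nor do the earlier safety signals show that exit tests are critical. Section 1.2.1 reports one significant liver-enzyme rise at 20 mg, not repeated at doses up to 180 mg. It also reports an average 3-fold D-dimer rise at Day 3 in subjects given 180 mg, which went down by Day 7. Completers have no scheduled laboratory tests between Day 1 and Day 28 either, so an exit sample would show that D-dimer pattern only in someone leaving in about the first week. Section 2.4 reports no serious adverse events associated with the highest dose tested. Treatment is a single session, so an exit result cannot inform a decision to stop dosing.

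Finally, the counts with the fix are maxima. Section 5.2.7 asks only for reasonable measures to hold the visit, and a subject who does not return gains nothing under either wording.

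**Conclusion.** The point holds in limited form. Section 5.2.7 names a specific template that suits completers and not early leavers, and following it exactly can leave a subject who exits between Day 1 and Day 28 with Day 1 laboratory and ECG values only and no post-dose examination. For exits between Day 28 and Day 56, the loss is the last vital signs and examination, and there is no assured recheck of an elevated laboratory value. After Day 56 nothing scheduled is lost.

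The counts assume that discretionary and event-driven rules add no tests; where sites use those rules, the gap is smaller. The documents do not support the stronger reading that leavers go without safety follow-up. Equally, they do not support treating the adverse event tables as immune, given 5.1.9 and 5.1.14. Efficacy, alpha and power are not affected. The size in subjects is unknown because no withdrawal rate is stated. The change is worth making for patient safety and for consistency across the 4 sites.

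**What to change.** Add to Section 5.2.7, for both phases:

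- A subject terminating before Day 28 has the Day 28 safety assessments at the termination visit: hematology, serum chemistry, urinalysis, ECG, vital signs and physical examination.
- A subject terminating between Day 28 and Day 56 has vital signs, a physical examination and a recheck of any elevated laboratory value.
- Results are listed as early-termination values.

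Two additions are optional. One is a full set for exits caused by an adverse event after Day 28, which would go beyond the planned schedule for those subjects. The other is a summary of last post-dose values, which would pool leavers' values from varying days with completers' values from Day 28 or Day 56.

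The cost is a short protocol paragraph and a slightly longer exit visit. The core change adds no tests beyond the planned schedule: before Day 28 it brings forward the Day 28 set, and between Day 28 and Day 56 it brings forward the Day 56 vital signs, examination and conditional recheck.

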5.2.8. Unscheduled Visit

Unscheduled visits will be performed upon investigator's discretion, upon Sponsor request to redo tests with unusual results or complete missing results and may occur upon subject's decision with no notification in advance. Unscheduled visits will include any study procedure deemed necessary, as described in Section 5.1.

6. DESCRIPTION OF THE OPEN LABEL EXTENSION PHASE OF THE STUDY

At study completion, the randomization codes will be opened. Nineteen (19) Subject who were injected with placebo will be offered to be treated with RZL-012.

At least 4 lipomas/nodules, preferably 6, and no more than 8, will be injected per subject. Dosing will be according to lipoma size, where the total injected dose will not exceed 240mg per patient (48 injections at 5mg/injection).

Dosing will be done according to lipoma size, as described in Table 6:

Table 6: Dosing of RZ-012 in the Open Label Extension Phase

Number of Subjects – Active/Placebo	19/19					
Lipoma/Nodule size – diameter (cm)	1-1.9	2-3.9	4-5.9	6-7.9	8-10	
Total Dose of RZL-012 in the RZL group (mg)	10	20	40	50	60	
Number of Injections	2	4	8	10	12	

The injection with RZL-012 will be done within 30 days of randomization codes opening.

The day that will be set up by the physician for RZL-012 injection will be the baseline visit, Day 0.

On this day, each subject will have the procedures, as described in Section 5.1:

Day 0- Physical exam, Clinical laboratory tests (hematology, chemistry) lipid profile and urinalysis, ECG, injection with RZL-012, concomitant medication, vital signs – before and after the injection, ultrasound measurement of the lipomas*, photography of the lipomas, QOL questionnaire, Draize score – before and after injection, pain score and AEs documentation.

Day 1 – ECG, vital signs, Draize score, clinical laboratory tests including urinalysis and lipid profile, AEs record.

Day 7 – Phone call visit. The study coordinator/nurse will call the subjects to ask about adverse events and general health.

Day $28\pm 2 - ECG$, physical exam, vital signs, clinical laboratory tests, urinalysis, Draize score, ultrasound measurement of the lipomas, photography of the lipomas, pain score and AEs documentation.

Day 56±2 - Physical exam, vital signs, ultrasound measurement of the lipomas, photography of the lipomas, Draize score, pain score and AEs documentation.

Day 84±2 - Ultrasound measurement of the lipomas, photography of the lipomas, QOL questionnaire, Draize score pain score, QOL questionnaire and AEs documentation.

Schedule of events of the open label extension part is presented in Appendix 2.

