4. STUDY POPULATION

4.1. INCLUSION CRITERIA

Subjects meeting all of the following criteria will be eligible for study participation:

- 1. Women and men, 18-70 years old.
- 2. At least 4 painful lipomas of appropriate size to be injected on a background of DD.
- 3. Generally considered healthy according to medical history, physical examination, electrocardiogram (ECG) and laboratory evaluation with an emphasis on metabolic parameters (fasting glucose concentration < 200 mg/dL).

- 4. Subjects must be able to adhere to the visit schedule and protocol requirements and be capable of completing the study.
- 5. Males or females in the age of fertility are willing to refrain from sexual activity or agree to use a double-barrier contraceptive device (e.g., condom and spermicide) for 4 weeks after treatment with RZL-012.
- 6. Subjects must sign an informed consent indicating they are aware of the investigational nature of the study.

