4.2. EXCLUSION CRITERIA

Subjects meeting any of the following criteria will be excluded:

- 1. Unable to tolerate subcutaneous injections.
- 2. Pregnant women.
- 3. Subjects with uncontrolled cardiac, hepatic, renal or neurologic/psychiatric disorders, that in the opinion of the investigator places the subject at significant risk.
- 4. Positive blood screen for Hepatitis B surface antigen (HbSAg), Hepatitis C virus (HCV), or Human immunodeficiency virus (HIV).
- 5. Subjects with a clinical history of active primary or secondary immunodeficiency, autoimmune disease or subjects taking immunosuppressive drugs such as corticosteroids.
- 6. Subjects with dysfunctional gallbladder activity, e.g. underwent cholecystectomy or cholecystitis.
- 7. As a result of medical review and physical examination, the PI (or medically qualified nominee) considers the subject unfit for the study.
- 8. Known sensitivity to components of the injection formulation.
- 9. Prior wound, tattoo or infection in the treated area.
- 10. Prior invasive treatment such as surgery or injectable drug at the RZL-012 injected area.
- 11. Subjects treated chronically at least 3 months prior to study entry with systemic steroids or immunosuppressive drugs.
- 12. Subjects treated chronically at least one week prior to study entry with Non-Steroidal Anti-Inflammatory Drugs (NSAIDs).
- 13. Current participation or participation within 3 months prior to the start of this study in a drug or other investigational research study.

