10.4. STATISTICAL ANALYSIS

10.4.1. General

All measured variables and derived parameters will be listed individually and, if appropriate, tabulated by descriptive statistics.

For categorical variables summary tables will be provided giving sample size, absolute and relative frequency and 95% CI (Confidence Interval) for proportions by study group.

For continuous variables summary tables will be provided giving sample size, arithmetic mean, standard deviation, coefficient of variation (CV%), median, minimum and maximum and 95% CI (Confidence Interval) for means of variables by study group.

All tests will be two-tailed, and a p value of 5% or less will be considered statistically significant.

Subject Disposition

A detailed description of subject accountability including count of subjects included, exposed, completed (i.e., subjects who complete the study treatment) and discontinued along with the main reason for discontinuation will be generated for each treatment group and for all subjects. All withdrawals from the study, taking place on or after study drug injection, will be fully documented in the body of the Clinical Study Report.

Note that the actual study duration is for a period of maximum 3.5 months, with efficacy analyses being conducted at Day 28, 56, and 84 visits.

At the end of the period, when the follow up of subjects will be completed, randomization codes will be opened.

Placebo subjects who would like to be treated with RZL-012 at the end of the study will be injected (within a period of 30 days from codes opening) and will be followed up for efficacy for additional 84 days. The efficacy information that will be collected for the open label extension study will not be included in the randomized double blinded study report but will be used for internal information.

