APPENDIX I: TRIAL SCHEDULE OF EVENTS

Study Procedure	Double	Double Blind, Randomized, Placebo Controlled			ects (wi	el exter ll be do tudy co	one wit	hin 30					
	Screening Day	Baseline (Treatment)	Visi	Visit Schedule (Days 1 to 84)					Visit Schedule (Day 0 to 84)				
Study Day	Day (-14) through Day (-1)	Day ^a 0	Day 1	Day 7	Day 28	Day 56	Day 84	Day ^d 0	Day 1	Day 7	Day 28	Day 56	Day 84
Signed informed consent	X												
Medical history	Х												
Physical Exam	Х				X	X		Х			X	Х	
Concomitant Medication	X	Х	Х	X	X	X	X	Х	Х	Х	Х	Х	Х
Pregnancy kit test (women) ^b		Х											
Vital signs	X	Pre ^c X post ^c	X		X	X		Pre ^c X post	Х		X	X	
Injection of RZL- 012/Placebo		Х						X					
ECG	Х		Х		Х			Х	Х		Х		
Serology assay	X												
Draize Score		Pre ^c X post ^c	X		X	X	X	Pre ^c X post c	Х		X	X	Х
Ultrasound measure of lipomas	X	Xe			Х	Х	X	х			Х	Х	X
Photography of lipomas	Х	Xe			Х	Х	X	x			X	Х	X
Serum chemistry and hematology	X		x		Х			Х	Х		Х		
Urinalysis	X		Х	1	Х		1	Х	Х	1	Х		

	Double	Double Blind, Randomized, Placebo Controlled							en Lab ects (wi of s		one wit	hin 30	
Study Procedure	Screening Day	Baseline (Treatment)	Visi	t Sched	lule (D	ays 1 t	o 8 4)		Visit Sc	chedule	e (Day	0 to 84)
Study Day	Day (-14) through Day (-1)	Day ^a 0	Day 1	Day 7	Day 28	Day 56	Day 84	Day ^d 0	Day 1	Day 7	Day 28	Day 56	Day 84
Lipid profile	X		Х					Х	Х				
Pain assessment of each lipoma		Х			Х	Х	X	Х			X	Х	Х
QOL questionnaire		Х					Х	Х					Х
AEs assessment		Х	X	Х	X	Х	X	Х	Х	X	Х	Х	Х

a. Day 0 defines the day of RZL-012/placebo injection in the double blinded randomized study

b. At screening visit women will be asked whether they are pregnant, test will be performed at baseline visit before dosing

c. Pre/post - refers to before/after injection, respectively

d. Day 0 defines the day of RZL-012 injection in the open label study

e. In case of screening visit that will be conducted only one day before Baseline, ultrasound and photography at Baseline visit is optional. The ultrasound parameters and photography collected at screening will be used at Baseline visit.

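### The open-label extension gives women their first RZL-012 dose without a scheduled pregnancy test, nominally 84 days or more after the only one.

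*Combined protocol and SAP*

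**What the plan says.** Section 4.2 lists "2. Pregnant women" among the exclusions. For the blinded phase, Appendix I footnote b says how this is applied: "At screening visit women will be asked whether they are pregnant, test will be performed at baseline visit before dosing". Table 4 agrees, with a pregnancy-test row timed at baseline. The Synopsis places both a pregnancy test and a confirmation of eligibility in the pre-treatment part of Day 0.

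The extension offers RZL-012 to subjects who received placebo. Section 6 gives the timing: "The injection with RZL-012 will be done within 30 days of randomization codes opening". On when codes open, Section 10.4.1 says: "At the end of the period, when the follow up of subjects will be completed, randomization codes will be opened". Section 6 then sets out the extension Day 0 procedures: "Day 0- Physical exam, Clinical laboratory tests (hematology, chemistry) lipid profile and urinalysis, ECG, injection with RZL-012, concomitant medication", followed by vital signs, ultrasound, photography, quality of life, Draize score, pain score and adverse events. Neither a pregnancy test nor a renewed eligibility check is listed.

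The contraception requirement in Section 4.1 is abstinence or a "double-barrier contraceptive device (e.g., condom and spermicide) for 4 weeks after treatment with RZL-012".

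**The concern.** The protocol excludes pregnant women and treats a test immediately before injection as the way to apply that exclusion. For a placebo subject, the dose that carries the risk is the extension dose, and that visit has no test. The one negative result on file was obtained before a vehicle injection, months earlier.

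The stakes are a possible fetal exposure to a drug with little relevant human experience. The dose may reach 240 mg, which Section 2.4 puts 33% above the highest dose given to humans and the Synopsis puts at 100% of the NOAEL. By the entry criteria in Table 1, the two obesity-programme trials enrolled men only, and the lipedema and Dercum's trial admitted women only if at least 2 years post-menopausal. This trial admits women aged 18 to 70 with no menopausal restriction. Treatment is a single session, so a missed check cannot be put right at a later dose. Section 9 has no procedure for reporting an exposed pregnancy, beyond naming a congenital anomaly as a serious outcome.

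**Working it through.** The plan states no figure for this point. The check compares the schedules and then counts days.

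**1. Pregnancy test at the dosing visit, by source**

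| Source | Blinded Day 0 | Extension Day 0 |
|---|---|---|
| Synopsis visit schedule | Listed, with eligibility confirmation | Not listed; no eligibility check |
| Section 6 | Not applicable | Not listed; no eligibility check |
| Table 4 / Table 5 | Row present in Table 4 | No row in Table 5 |
| Appendix I | One mark in the row | No mark in the extension columns |

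The test is missing from two prose lists and two tables, so damaged table extraction does not explain it.

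**2. Could another procedure cover it?**
- Section 6 points to Section 5.1 for its procedures. Section 5.1 describes no pregnancy test.
- The chemistry (5.1.9.2) and urinalysis (5.1.9.3) panels contain no hCG.
- Section 6 refers to Appendix 2 for the extension schedule, but Appendix II is the pain scale. Appendix I is the only schedule.
- Unscheduled procedures (5.2.8) are discretionary.

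**3. Age of the last scheduled test at extension dosing**

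Gap = time to the Day 84 visit + wait for code opening + 0 to 30 days to injection.
- Nominal, last subject to finish, codes opened at that visit (assumption): minimum 84 + 0 + 0 = 84 days; maximum 84 + 0 + 30 = 114 days.
- With the ±2-day visit window (5.2.6): 82 + 0 + 0 = 82 days to 86 + 0 + 30 = 116 days.
- Earlier subjects, if codes open only when everyone's follow-up is complete: add the time to the last subject's final visit. The enrolment period is not given. Assuming a spread of 0 to 12 months, the longest gap runs from 116 days to about 116 + 365, or roughly 480 days.

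**4. Time with neither required contraception nor a test**

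If the 4-week rule is applied after the blinded injection, it ends at day 28. The uncovered period before extension dosing is then at least 82 − 28 = 54 days, or 84 − 28 = 56 days nominally. Read literally, the rule runs from RZL-012 treatment and would not apply to a placebo subject before the extension at all.

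**5. Number of women**

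Section 1.1.1 gives a female-to-male ratio of 6 to 1. Applied to 19 placebo subjects, 19 × 6/7 = 16.3, or about 16. This counts all women and assumes that everyone opts in.

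**The case against.** The best counter-reading is that the safeguard exists in general text. Section 6 calls the extension injection day a baseline visit. Section 5.2.5, on the baseline visit, says that eligibility is confirmed before dosing. Footnote b places the test at the baseline visit before dosing, and nothing in Section 6 lifts exclusion criterion 2. On that view the lists are merely incomplete.

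This does not hold up as a safeguard. Section 5.2.5 also speaks of completing the screening evaluation, which belongs to the blinded phase. Table 5, the extension's own table, sits in that section without the test. Footnote b starts from the screening visit, and its row has a single mark, under blinded Day 0. It is fair to say that the protocol nowhere permits dosing a pregnant woman; what is missing is the step that would detect the pregnancy.

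Some points about size do stand:
- The strict minimum gap is 82 days, not 84, and the last subject's maximum is 116, not 114.
- The figure of 16 is an upper-end illustration from a disease sex ratio. The number of women of childbearing potential is not given and is probably well below it.
- The longer wait for earlier subjects rests on Section 10.4.1. Section 2.3 can be read as code opening 84 days after each subject's own dose.
- The effect on extension reporting is secondary. No randomised comparison, power or error rate is affected.

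The Synopsis screening line might imply a second test, but it would fall before blinded Day 0 and would not shorten the gap.

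**Conclusion.** The concern holds. All four descriptions of extension Day 0 omit the pregnancy test that the blinded phase requires, and no other scheduled procedure replaces it. A site that followed the extension schedule exactly could give a pregnant woman her first RZL-012 dose. The most recent test would be 82 to 116 days old for the last subject, assuming codes open at that subject's final visit, and possibly much older for those enrolled early. At most 19 subjects are involved, and the number of women at actual risk cannot be worked out from the protocol. An investigator may well test anyway, but nothing scheduled in the extension requires it. This is a patient-safety omission and should be corrected before any extension dosing.

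**What to change.** Add a pregnancy test for women, done before injection, to extension Day 0 in the Synopsis, Section 6, Table 5 and the extension columns of Appendix I, and extend footnote b to both dosing visits. In the same amendment, state that the exclusion criteria are re-checked before the extension injection, and consider requiring contraception from the offer of RZL-012 until the extension dose, in addition to the 4 weeks after it. The kit test is already a trial procedure, so the cost is amendment wording and one kit per woman entering the extension, at most 19. The design, the sample size and the analysis of the blinded phase are unchanged.
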